# 4.4. Workstream 2: Developing measures of nurse staffing requirements based on routine data

This workstream aims to **develop and test algorithms** to estimate nurse staffing requirements from routinely available patient data. Since there is no "gold standard" for measuring nurse staffing requirements, in the first instance we will aim to replicate measurements using the NICE-recommended Safer Nursing Care Tool, which is in use in most English hospitals. This tool bases its estimates on a categorisation of patients on the ward into acuity/dependency groupings, with estimates of direct care time for these patients as well as allowances for other work associated with patients (indirect care) and other administrative tasks. Adjustments to account for differences in this allowance are currently left to professional judgement. We will extend our approach to attempt to capture some of these workload aspects beyond acuity/dependency, while recognising that not all elements of work are measurable.

We will develop two broad approaches using data that is already recorded to replicate the results of SNCT assessments: i)replicate **individual** patient acuity/dependency classifications and ii) replicate the staffing requirements for a **whole ward**. For i), where Trusts record individual SNCT ratings we will seek to develop models based on rich individual data from electronic patient records and care plans. However, given that staffing decisions are generally made based on the whole ward as nurses care for several patients each, we will also aggregate these to a ward level (ii). It is possible that inaccuracies in individual categorisations may have little impact on overall estimates when aggregated to a ward level. Furthermore, some Trusts record only counts of patients per SNCT category,

Ethics/ERGO no: 100780; IRAS no: 346148

which cannot be linked to individuals, so for these Trusts we can only follow approach ii) and estimate ward staffing requirements directly.

We will consider staffing decisions at **different timepoints**, such as daily deployment and redeployment decisions and twice-yearly establishment review (as specified in NICE guidance). The priorities will be determined based on the national survey and user needs identified in the first set of workshops in workstream 1. Some information is not known in real-time, so we will use different predictor variables depending on the timing of the decision. We will assess the predictive accuracy of the algorithms we derive, as well as assessing the feasibility of applying algorithms to datasets from other hospitals and test their external validity.

#### 4.4.1. Data sources

The **data sources** are a range of hospital systems which will differ by Trust. The Safer Nursing Care Tool data that is collected twice-yearly for establishment reviews will be sourced from the relevant spreadsheets/Trust records, and where available the SNCT data that is recorded for deployment decisions will be extracted from the electronic roster (RLDatix SafeCare system). Patient data will be sourced from various IT systems storing patient administration records, nursing care documentation, care plans, pharmacy and surgery records. We will supplement this with contextual information about wards sourced directly from our Trust nursing contacts.

#### 4.4.2. Sample sizes

For **developing the algorithms**, we will use retrospectively collected data from our two partner Trusts. Since the new version of the SNCT launched in October 2023, we will extract data from this date onwards or from when the new tool was embedded in the Trusts. We aim to collect at least one year of data. This covers two staffing establishment reviews where acuity/dependency scores are recorded for at least 30 days, so there will be a minimum of 60 (30 x 2) days' data per ward, although in many wards they collect data much more frequently giving about 730 (2 times per day x 365) data points per ward. Scaled up across wards and two Trusts this will give us in the region of 4,800-58,400 ward shift data points for the ward-level approach (assuming 40 wards per Trust), and approximately 120,000-1,460,000 patient shift data points for the patient-level approach (assuming on average 25 patients per ward). For **external validation** of the algorithms, we will use data from at least three further Trusts, and more recent data from our two partner Trusts (data covering at least 1 year).

#### 4.4.3. Variables

Our **outcome variables**, which we are trying to predict, are all based on the Safer Nursing Care Tool assessment of staffing requirements. This is the overall nurse staffing requirement for a ward, which will include registered nurses, nursing associates and support workers (although note job titles vary between wards and Trusts), but will exclude managers who are not providing any direct care to patients. For individual patient predictions of staffing needs, the outcome variable is the acuity/dependency category (or the related workload multiplier). This is a categorical variable with 7 possible values. For ward-level predictions of staffing needs, the outcome variable is whole-time equivalents (WTE) per patient. This is calculated by multiplying the number of patients in each category with the corresponding multiplier, adding together and dividing by the number of patients. This can be calculated for each shift or time period that the SNCT data is recorded. There are different

Ethics/ERGO no: 100780; IRAS no: 346148

multipliers dependent on ward type and ward configuration (e.g. separate multipliers for admissions units and wards with all single rooms). For deployment decisions we can remove the uplift (for leave) and convert WTE to care hours on a day/shift, to calculate a care hours per patient measure.(7)

In terms of **predictor variables**, we will derive a set of variables that are likely to relate to patient acuity/dependency categorisations as assessed by the SNCT. We will be guided by the SNCT acuity/dependency level descriptions alongside expert judgement (JB, SW, SO) to decide which characteristics are important to consider. Routinely available data in the patient electronic record includes demographics, information about the patient journey (admission, ward transfers, discharge) and diagnostic/procedure information. Where available, we will consider variables from care plans and care documentation. These include records of infusions, oxygen, specialing needs (one-to-one supervision), observations, and moving and handling assessments. JB has already mapped variables from care documentation onto acuity/dependency categories, so we will build on this work. We will also investigate the possibility and feasibility of including variables from pharmacy and surgery datasets such as numbers of medicines, anaesthesia type/time and surgery times. For the ward-level approach, either we will predict the individual's acuity/dependency category and then aggregate into a ward-level prediction, or where individual ratings are not available, we will transform patient-level variables into ward-level variables e.g. proportion of patients who are male, average age, etc.

Depending on which staffing decision our algorithm is supporting, we will consider the **timeliness** of data, and correspondingly, different variables will be used. For example, establishment reviews can make use of retrospective data, while decisions about redeployments at the start of a shift can only use information available in real-time. We will carefully consider, informed by discussion with our nursing and IT system team members (SW, TW, JB), which variables are likely to be available in near real-time versus retrospectively. Where possible we will obtain timestamps for when data were recorded to help with this. Some variables will change over the course of a patient's stay while others are fixed. Relevant information that is known at admission includes age group, gender, method of admission, long-term conditions and admission diagnosis. Information that changes over the course of the stay includes vital signs, treatments and therapies, length of stay, number of transfers and complications. Further variables that are available retrospectively include procedure codes (HRGs), discharge destination and overall length of stay. Information from prior admissions for the same patient could also be incorporated.

Based on discussions with nurses in WS1, we will explore whether we can **extend** our algorithms to address **skill mix**, if this is deemed an important issue. While the SNCT does not provide a recommendation for the skill mix, we will attempt to predict how many Registered Nurses versus how many Support Workers are needed. For this, as a starting point, we will look into segmenting our predictions into acuity versus dependency, with a starting assumption that wards/patients with higher acuity need a higher proportion of Registered Nurse time and wards/patients with higher dependency need a higher proportion of Support Worker time. We recognise the limitations of this assumption given that there are elements within the dependency categories that require Registered Nurses such as delivery of complex infusions, wound management, end-of-life care and complex discharge planning. We will also factor in Nursing Associates, in a subgroup analysis for wards where there is enough data to draw meaningful conclusions.

Ethics/ERGO no: 100780; IRAS no: 346148

We will extend our measure to incorporate other aspects of nursing workload that are unrelated to acuity or dependency. This includes both those workload drivers that are currently left to "professional judgement" when using the SNCT, e.g. high rates of admissions/discharges or unusual ward layouts(42) as well as those that are captured by distinct sets of SNCT multipliers (e.g. Acute Admission Unit multipliers, single room multipliers).(43) Here we will work closely with our nursing co-Investigators and advisors, and review available literature to determine which candidate variables to include.(44, 45) We will make use of contextual ward information from ward managers to understand ward layouts including numbers of funded beds, rooms and single rooms.

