#### 4.4.4. Data analysis

The data linkages between datasets are complex but our team have prior experience with this (PM, CS, CDO, PG). Data will be processed and linked differently according to approach (patient- versus ward-level, establishment versus deployment decisions). For the patient-level approach, for example, all patient information pertaining to one admission will be linked together, and linked with the acuity/dependency category of the patient (repeated for each time the patient is assessed on the ward). Then these predictions will be aggregated to a ward level. In contrast, for the direct ward-level approach, the variables derived are case-mix variables. This will involve identifying which patients are staying on the ward and linking information about those patients together. To calculate the Safer Nursing Care Tool measure, for each assessment we will calculate the ward staffing requirement using the SNCT multipliers and the counts of patients per acuity/dependency category, and translate this into a per patient measure, whole-time-equivalents per patient (for establishment) or care hours per patient (for deployment). We will consider alternative approaches for how to deal with changing patient information, e.g. where a particular care activity is not recorded every day (missing data), whether to assume it is still needed or not.

In **machine learning** terminology, predicting individual acuity/dependency categories is a classification problem, since there are only limited choices, while predicting ward-level staffing requirements is a prediction problem, since the outcome is continuous. Thus different techniques are likely to be appropriate for these two problems. For the individual-level classification problem, we will begin by implementing ordered logistic regression. Additionally, we will explore using decision trees, random forests(46) and support vector machines, which are well-suited for handling categorical data with a limited number of outcomes. For ward-level regression prediction, we will start with simple approaches like linear regression before extending to other approaches if we meet challenges. We will consider GAM models,(47) random forests, support vector regression, gradient boosting, neural networks, etc., based on the suitability of the data.(48)

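### Adding up each patient's most likely category can bias the ward total, in a direction and size that vary by ward; the protocol should aggregate expected multipliers instead

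*Protocol*

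**What the plan says.** Protocol section 4.4 sets out two routes to a ward requirement: model individual patients and aggregate, or model the ward directly. For the first route, section 4.4.3 states that "the outcome variable is the acuity/dependency category (or the related workload multiplier" (the multiplier is given in brackets as an alternative) and adds "This is a categorical variable with 7 possible values". The ward requirement is defined there by "multiplying the number of patients in each category with the corresponding multiplier, adding together and dividing by the number of patients". For the link between the two levels the same section says "either we will predict the individual's acuity/dependency category and then aggregate into a ward-level prediction", and section 4.4.4 repeats "Then these predictions will be aggregated to a ward level".

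Section 4.4.4 treats the patient-level task as classification: "For the individual-level classification problem, we will begin by implementing ordered logistic regression". Decision trees, random forests and support vector machines follow. On the error that aggregation carries, section 4.4 offers one sentence: "It is possible that inaccuracies in individual categorisations may have little impact on overall estimates when aggregated to a ward level".

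Agreement with the Safer Nursing Care Tool (SNCT) is to be judged by Bland-Altman limits and root mean squared error (RMSE), in training and test data and again in at least three further Trusts.

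**The concern.** A classifier that returns one category per patient returns the most probable one. A category that is uncommon for every predictor pattern is then hardly ever returned, although it contributes to the true total in proportion to its frequency and its multiplier. Random individual errors cancel as patients are added up. This error does not, because it is the gap between the multiplier of the likeliest category and the mean multiplier given the predictors.

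Three uses of the results are exposed:

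- The patient-level route could lose to the direct ward-level route because of its decision rule, not because of its information.
- Ward rankings and performance in external Trusts could shift with case mix, and this could be mistaken for poor transportability.
- If such a measure went forward to Workstream 3, a ward-dependent error would sit inside the staffing deviation, which is the exposure there.

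**Working it through.** **The plan's own figures.** Section 4.4.2 assumes 2 Trusts, 40 wards each, 60 to 730 assessments per ward and 25 patients per ward.

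- Ward shifts: 2 x 40 x 60 = 4,800 and 2 x 40 x 730 = 58,400.
- Patient shifts: 4,800 x 25 = 120,000 and 58,400 x 25 = 1,460,000.

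All four agree with the text. The protocol gives no multiplier values, category frequencies or misclassification rates, so the bias cannot be computed from the document alone.

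**The error in formula.** Let p_k be the probability of category k given a patient's predictors, and m_k its multiplier. The expected requirement is the sum over k of p_k x m_k. The assigned-category rule uses m of the category with the largest p_k. Per patient:

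- systematic part: b = m(likeliest category) - sum of p_k x m_k;
- random part: the patient's true multiplier minus sum of p_k x m_k, which has mean zero.

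Averaged over 25 patients, the standard deviation of the random part is divided by the square root of 25, that is by 5. The average of b is not reduced. For the 30-day establishment samples (30 x 25 = 750 assessments) the divisor would be at most about 27, and less in practice because the same patients recur. Again b is untouched.

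**Simulation.** A correctly specified ordered-logit model with 7 categories was applied to 40 wards x 300 shifts x 25 patients, with 0.3 of the predictor variance between wards. Assumed inputs, none of them from the protocol:

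- multipliers, wide set: 1.0, 1.3, 1.6, 1.9, 2.2, 3.5, 6.0;
- multipliers, narrow set: 1.0, 1.2, 1.4, 1.6, 1.8, 2.2, 3.0;
- five category mixes, with the top category at 0.5% to 1%;
- latent R2 of 0.2, 0.5 and 0.8.

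This gives 5 x 2 x 3 = 30 scenarios. Bias of the ward total from assigned categories, at R2 0.2 / 0.5 / 0.8:

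| Commonest category | Wide multipliers (%) | Narrow multipliers (%) |
|---|---|---|
| Lowest | -24.9 / -10.8 / -3.9 | -16.4 / -7.3 / -2.1 |
| Third | -6.9 / -5.2 / -2.1 | -3.4 / -2.6 / -0.7 |
| Lowest and fourth | -0.4 / -2.0 / -1.2 | +1.1 / -0.5 / -0.2 |
| Fourth | +3.6 / +0.1 / -0.4 | +4.2 / +1.0 / +0.2 |
| Fifth | +6.7 / +0.8 / -0.5 | +7.4 / +2.7 / +0.4 |

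Probability-weighted totals were biased by -0.1% to +0.1% in all 30. At R2 0.2 and 0.5 the top category was assigned to 0% to 0.1% of patients.

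**Two rows by hand** (wide multipliers, R2 0.2):

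- *Third category commonest.* Assigned shares: 0.073 in category 1, 0.901 in category 3, 0.026 in category 5. Mean assigned multiplier: 0.073 x 1.0 + 0.901 x 1.6 + 0.026 x 2.2 = 1.572. A bias of -6.9% implies a true mean of 1.572 / 0.931 = 1.688. The commonest multiplier, 1.6, lies below it. Per 25 patients: 25 x (1.572 - 1.688) = -2.9 WTE.
- *Fifth category commonest.* Assigned shares: 0.086 in category 1, 0.914 in category 5. Mean: 0.086 x 1.0 + 0.914 x 2.2 = 2.097. A bias of +6.7% implies a true mean of 2.097 / 1.067 = 1.965. The commonest multiplier, 2.2, lies above it. Per 25 patients: 25 x (2.097 - 1.965) = +3.3 WTE.

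**Between wards.** With the fourth category commonest, wide multipliers and R2 0.5, the overall bias was +0.1%, yet individual wards ran from -8.0% to +2.3%.

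**Precision.** In a separate set of 18 scenarios, also on assumed inputs, the bias from assigned categories ran from -25% to +7%, and ward-level RMSE was higher than with probability weighting in all 18.

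**The case against.** The strongest reply is that the protocol does not commit to summing labels. Section 4.4.3 admits the multiplier as the patient-level target, and a model for its mean avoids the problem. Ordered logistic regression, the stated starting point, supplies probabilities. This is correct, and the point is conditional for that reason. However, the text speaks only of predicting a category and then aggregating, calls the task classification, and lists support vector machines, whose basic output is a label. The multiplier alternative is followed at once by a description of the outcome as categorical. Probability weighting and calibration appear nowhere.

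A second reply is that the planned checks would expose a bias. Bland-Altman gives the mean difference directly, agreement is reassessed in other Trusts, and only the leading algorithms enter Workstream 3. This stands for an overall bias. It stands less well where wards err in opposite directions: with an overall +0.1% and wards from -8.0% to +2.3%, the mean difference shows almost nothing. Wider limits would hint at trouble without locating it, and no correction is stated.

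A third reply is that probability weighting looks this good only because the simulation predicts from the true model. That is fair. With poorly calibrated probabilities, or case mix that differs in the external Trusts, it too can be biased.

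A reader might also infer that the patient-level route would understate staffing need. The document does not support a direction. Uncommon low categories are under-picked as well, and several plausible mixes give overstatement. Nor does the protocol assume that individual errors vanish: its sentence in section 4.4 raises only a possibility.

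**Conclusion.** The point holds in conditional form. If assigned categories are summed, the ward requirement can be systematically biased and the bias can differ between wards, so the possibility that "inaccuracies in individual categorisations may have little impact on overall estimates when aggregated to a ward level" is not assured. Weak prediction makes it worse: the illustrative range of -24.9% to +7.4% comes from R2 0.2, and at R2 0.8 it narrows to -3.9% to +0.4%. The sign follows the position of the commonest category relative to the mean multiplier mainly when prediction is weak. At R2 0.8 with wide multipliers, the fourth- and fifth-category mixes gave -0.4% and -0.5%.

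Size and sign rest wholly on assumed multipliers, mixes and predictive strengths. The document does not support a claim that need would be understated, or that a biased measure would necessarily reach Workstream 3. The mechanism does not depend on those particular inputs, and the better rule is nearly free. This is a cheap improvement, not a flaw that undermines the study.

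**What to change.** Add to section 4.4.3 or 4.4.4 that ward-level predictions from patient-level models are the sum over patients of calibrated category probabilities times the multipliers applicable to that ward type, divided by the number of patients where a per-patient figure is wanted. Alternatively, state that the multiplier itself is the patient-level target and is modelled as a mean.

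Report ward-level mean bias by ward type and by Trust beside the Bland-Altman limits and RMSE. Keep category accuracy as a patient-level statistic only, and do not use it to choose the ward-level method.

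The cost is a sentence or two and no new data. Decision trees, random forests and support vector machines need a calibration step, and calibration should be rechecked in the external Trusts and in the later data from the partner Trusts.

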#### 4.5.2. Variables

We will consider a range of **patient outcome variables**. Our primary patient outcome is mortality within 30 days of admission, as it has a strong association with staffing levels.(5, 17) Other patient outcomes we will model include length of stay, readmissions within 30 days (which both have high strength of evidence for an association with staffing levels according to a recent review)(4) and healthcare-associated conditions such as pneumonia and pressure ulcers (which have moderate evidence).(4) We will limit the latter analyses to surgical patients since for medical patients it is harder to distinguish between complications and conditions present on admission.

Our other outcomes are measures of **perceived staffing adequacy** assessed through the prospective micro-survey. We will ask clinical nurses three questions as in our previous study: i) Were there enough staff for quality?, ii) Were breaks missed? and iii)Was care left undone?(13) These were derived following pilot work of a more extensive set of questions, and are aimed to be quick to answer and give a good indication of overall staffing adequacy on a ward. In our previous study these were all associated with deviation from SNCT-recommended staffing.(13)

Ethics/ERGO no: 100780; IRAS no: 346148

Our **independent variables** are the deviation of actual staffing from measures of staffing required. In other words, under-/over-staffing compared to different measures of what is needed. Actual (achieved) staffing is measured as total care hours per patient day and includes all nursing staff on the ward: both Registered Nurses and Support Workers, both permanent and temporary (bank or agency) staff. Required staffing will be measured in different ways including: using the SNCT, current ward establishments, algorithmic measures (including the ward-level and patient-level approaches).

To start with we will model overall staffing but where possible will also consider **skill mix** by splitting out staff groups. We will use current ward establishments to calculate the planned skill mix and apply these to our alternative measures of staffing requirements. This will allow us, for example, to assess Registered Nurse understaffing and Support Worker understaffing separately, which is important since differing relationships have been found with patient outcomes.(5) We will use the pay band to categorise staff, given the differences in roles and job titles between Trusts.

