#### 4.5.3. Data analysis

This workstream will involve further **data linkages**. For each ward and shift or 24-hour period, we will calculate the actual staffing and the staffing requirements according to the most promising algorithms, as well as according to the SNCT. These will be converted to care hours per patient day. This requires working out which staff shifts and which patient stays overlap with each time period, as well as calculating the staffing requirements based on patients on the ward in each period. Then for each patient admission, we will link the understaffing/overstaffing they experienced during their hospital stay with their outcomes. Separately for each period we will link ward understaffing/overstaffing with measures of perceived staffing adequacy (from the micro-survey).

We will use **regression modelling** to assess the relationship between deviation from staffing requirement (measured in different ways) and outcomes. Depending on the nature of the outcome variable we will fit the appropriate model type (e.g. survival model for mortality, logistic regression for hospital-acquired conditions and perceived staffing adequacy). Our longitudinal data will allow us to explore how staffing over a patient's stay affects outcomes, since effects of low staffing may accumulate; we will consider approaches such as moving averages and exponentially weighted moving averages.

We will assess intra-cluster correlation coefficients to see whether there are unmeasured differences between wards. If appropriate, we will use multi-level regression models to assess how relationships differ between wards and hospitals, which can be used as an indicator of good/poor fit of a staffing measure, as in our previous work.(52) Specifically, random intercepts models can help us estimate, for each ward, the probability of the nurse in charge reporting enough staff for quality when staffing matches the measured staffing requirement. On the other hand, random slopes models can indicate for which wards relationships are in the same/opposite direction to what is expected.

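### Retrospective algorithm versions may use overall length of stay and discharge destination as predictors, and nothing keeps them out of validation against outcomes that those variables are or may encode

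*Protocol*

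**What the plan says.** Protocol 4.4.3 sorts candidate predictors by when they become known. One group changes during the stay: "Information that changes over the course of the stay includes vital signs, treatments and therapies, length of stay, number of transfers and complications". Another is known only afterwards: "Further variables that are available retrospectively include procedure codes (HRGs), discharge destination and overall length of stay". The only limit on later information concerns one type of decision: "decisions about redeployments at the start of a shift can only use information available in real-time". Establishment reviews are expressly allowed retrospective data. For the patient-level approach, 4.4.4 says that "all patient information pertaining to one admission will be linked together" and joined to each acuity/dependency rating.

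Workstream 3 then tests the algorithms. In 4.5.2, "Our primary patient outcome is mortality within 30 days of admission", and "Other patient outcomes we will model include length of stay, readmissions within 30 days", with healthcare-associated conditions in surgical patients added. The exposure is actual staffing minus required staffing. For each ward and period, 4.5.3 will "calculate the actual staffing and the staffing requirements according to the most promising algorithms", and each admission's own outcome is linked to the deviation met during that stay. The introduction to 4.5 treats lower risk with more staffing relative to a measure as the expected sign of validity. Section 4.5.3 ranks the measures by AIC.

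**The concern.** If the required staffing for a patient's ward is computed partly from how that patient's stay ended, the exposure contains the outcome. A patient with a long stay raises the ward requirement on every day of the stay, including the early days, so those days look short of staff. A regression of length of stay on shortfall then finds an association that the construction put there. The same can happen for death and for complications if the predictors carry them.

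Objective 3 of the protocol is this validation, and section 5 makes a further funding bid depend partly on how the algorithms relate to patient outcomes. A favourable patient-outcome result from a retrospective version could not be interpreted.

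**Working it through.** **1. Predictors and outcomes side by side**

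| Predictor information (4.4.3) | Known when | Workstream 3 outcome (4.5.2) | Overlap |
|---|---|---|---|
| Overall length of stay | After the stay | Length of stay | Same variable |
| Discharge destination | After the stay | 30-day mortality | Only if it has a code for death (not stated) |
| Diagnoses or complications coded after the scored shift | After the shift | Pneumonia, pressure ulcers | Encoded if used; 4.5.1 identifies adverse outcomes from diagnosis codes |
| Length of stay to date, events already recorded | At the shift | – | Legitimate, except a complication that is itself the outcome |
| – | – | Readmission, three micro-survey items | Not directly encoded |

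**2. Scale of the analysis.** The Workstream 3 sample-size text scales 626,313 admissions (5 years, 4 Trusts) to 5 Trusts over 9 months: 626,313 / 5 / 4 × 5 × 0.75 = 117,434. The plan says about 100,000. That is a loose rounding and not an issue here.

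**3. Null simulation, leak weights imposed.** From the protocol: 5 Trusts × 20 wards = 100 wards, 25 patients per ward, 9 months (274 days), giving about 100,000 admissions. Assumed: 2.9% deaths; actual staffing with mean 7.0 h and daily SD 0.8 h, independent of every outcome.

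- Clean requirement = 7.0 + 0.7 × admission severity.
- Leaky requirement = clean + *d* (if the patient dies) + *w* × (log length of stay − log 5).
- Exposure = actual minus ward-mean requirement, averaged over at most the first 5 days.
- Models: logistic for death, linear for log length of stay, both adjusted for severity. Means of three runs. AIC gain is over the clean algorithm.

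| *d* (h) | *w* | Between-ward SD of log stay | Death OR per extra hour (z) | AIC gain | Log-stay slope (z) | AIC gain |
|---|---|---|---|---|---|---|
| 0 | 0 | 0.3 | 0.978 (−0.5) | 0 | −0.004 (−0.7) | 0 |
| 0 | 0.3 | 0.3 | 0.985 (−0.4) | 0 | −0.128 (−25.8) | 668 |
| 1.0 | 0.3 | 0 | 0.807 (−5.0) | 24 | −0.029 (−6.0) | 36 |
| 1.0 | 0.3 | 0.3 | 0.821 (−4.8) | 22 | −0.126 (−25.6) | 656 |
| 0.5 | 0.1 | 0.3 | 0.891 (−2.7) | 7 | −0.047 (−9.2) | 83 |

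The clean requirement recovers the null. A leak through length of stay alone leaves death untouched but gives a slope of −0.128, that is exp(−0.128) = 0.88, an apparent 12% shorter stay per extra hour. With no between-ward differences in stay, the slope in the third row is −0.029, or exp(−0.029) = 0.97. These z values ignore ward clustering.

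**4. Hand check for death.** An extra 1.0 h for one of 25 patients raises the ward mean by 1/25 = 0.04 h. The log odds ratio is roughly that difference divided by the exposure variance. The simulated value, ln(1/0.807) = 0.214, implies a variance of 0.04/0.214 = 0.19. The staffing noise alone gives 0.64/5 = 0.13 for a five-day window and 0.64 for a one-day window, so 0.19 is plausible. Averaging over the ward dilutes the leak but does not remove it.

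**5. Algorithm fitted to SNCT ratings, with SNCT as comparator.** The plan trains on SNCT, so the weights are not free. Two further null simulations allowed for this, again with assumed inputs.

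- Length of stay, clustered errors: the leaky algorithm showed a spurious association with z of about 3 to 10. Its AIC was better than the clean algorithm's by 26 to 746, and better than SNCT's by 2 to 85.
- Death (200 wards × 25 beds, 274 days, about 135,000 stays, 3.2% deaths, death code among the predictors), OR per hour of shortfall:

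| SNCT excess given to patients who die | SNCT | Leaky algorithm | AIC |
|---|---|---|---|
| 1 h throughout the stay | 1.15–1.16 | 1.16–1.17 | Identical |
| 2 h throughout the stay | 1.32 | 1.34–1.35 | Gap 3–4 |
| 2 h in the last 3 days only | 1.15–1.16 | 1.07–1.08 | SNCT better by about 20 |

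**The case against.** The strongest reply is that the algorithm is trained to reproduce SNCT ratings. It can give extra hours to patients who die or stay long only so far as SNCT already does. Step 5 bears this out for mortality: most of the artefact belongs to any acuity-based requirement that includes the index patient, and SNCT carries it to the same degree or more. This stands, and it removes any general claim that the leak makes the algorithm beat SNCT. It does not remove the length-of-stay result, where the outcome is itself a candidate predictor.

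Second, 4.4.3 lists available information and not a final predictor set. It promises timestamps and predictors matched to each decision. Workstream 3 also scores shifts or days in care hours, which points towards deployment versions. That is fair, and a statistical analysis plan not at hand may settle the set. But the protocol itself names the candidates, the outcomes and the test of validity. It bars later information only for start-of-shift redeployment and does not confine Workstream 3 to such versions.

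Third, "treatments and therapies, length of stay, number of transfers and complications" can be read as another leak. It is not one as written: the sentence describes what is known so far in the stay, which is legitimate when a shift is scored. The exception is a complication that is itself the outcome being modelled.

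**Conclusion.** The point holds for algorithm versions with retrospective predictors that are tested against patient outcomes. The overlap is explicit for length of stay. It is conditional for mortality (discharge destination must record death) and for healthcare-associated conditions (codes recorded after the scored shift must be used). With no staffing effect, the plan as written can yield an association in the expected direction and a better AIC. The size depends on fitted weights that nobody yet knows, and every simulated figure rests on assumed weights, death rates and ward variation. Under those assumptions the length-of-stay artefact is clear against a clean algorithm and ranges from negligible to material against SNCT.

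A reader might infer more, and the documents do not support it:

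- That the algorithm could pass the whole of Workstream 3 with no staffing effect. Readmission and the three micro-survey outcomes are not directly encoded.
- That the leak must favour the algorithm over SNCT. For mortality it may give no advantage, or a disadvantage.
- That the spurious odds ratios can be set against the 9% in section 2.3. That figure is a hazard increase for staffing below the SNCT level, not an odds ratio per hour.

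**What to change.** Add a rule to 4.5.3: any algorithm version tested against a patient outcome uses only information recorded before the period being scored, and excludes any predictor that is or encodes that outcome. Overall length of stay, discharge destination, and retrospectively coded diagnoses or procedures are the examples to name. Length of stay to date and events already recorded may stay in, except a complication that is the outcome being modelled. Versions with retrospective predictors would be assessed only on agreement with SNCT and on the micro-survey.

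Leaving the index patient out of the ward requirement is useful as a sensitivity analysis, applied to the SNCT measure as well. It does not replace the rule, because between-ward differences in length of stay would remain.

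The cost is a few sentences and one extra prediction run. The downside is that retrospective versions get no validation against patient outcomes.
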